5.0 Study Procedures

The intervention period will last 3 months. The baseline outcome assessment will be conducted in person or virtually (via Microsoft Teams or over the phone) and in a private space. All other outcomes will be completed in person, virtually, or mailed. If the interview is completed in person or on the phone it will occur in a private space. *Upon approval of the June 27, 2022 (A033) amendment, the study team will no longer complete 6-month interviews for participants who enroll after this date.* The length of follow-up and schedule of outcome assessments at 1, 3, and 6 months (6-months pre A033 only) (see table 2 below) are to detect three types of treatment effects: 1) "early response" (at 1 month); 2) immediate post-intervention benefits at 3 months; and 3) sustained effects at 6 months post-randomization (3 months post-intervention). Study subjects (Veterans) will be reimbursed \$25 per completed outcome assessment (with 4 scheduled assessments each (baseline, 1, 3, and 6 months). Completion/payment of 6-month interviews will be for those enrolled prior to A033 approval only.

Table 2: Outcome Assessment Protocol: Measures and Schedule of Administration

Domain	Measure	Items	Time (min)	Schedule			
				BL	1 mo	3 mo	6 mo
Covariates	Demographics; disability compensation, comorbidity;	36	10	X			

	range of motion, treatments, BMI, medication list						
Neck pain disability	Neck Disability Index	10	3	X	X	X	X
Pain Severity	Brief Pain Inventory	10	3	X	X	X	X
Pain Interference	PROMIS—pain	4	1	X	X	X	X
Psychological	PHQ-9 Depression	9	2	X		X	X
	PROMIS-Depression	9	2	X		X	X
	GAD-7 Anxiety	7	2	X		X	X
	VA PTSD Screener	4	1	X		X	
	PTSD-PCL-17 (if screen positive)	17	5	X		X	
	Stress	10	3	X		X	
Generic HRQL	Medical Outcomes Study VR-36	36	10	X	X	X	X
Sleep	MOS Sleep Scale	12	3	X		X	
Somatic	Somatic Symptom Scale-8	8	3	X		X	X
	SSD-12	12	4	X		X	X
Pain beliefs	Pain Catastrophizing Scale	13	3	X		X	
Social support	Social Support Scale	12	2	X		X	
Treatment satisfaction	Pain-specific satisfaction	3	2		X	X	X
Intervention credibility	EXPECT Questionnaire	4	2	X		X	
Perceived Response	Global Impression of Change	1	1	X	X	X	X

Therapist-treated massage

Participants randomized to the therapist-treated massage (TT-M) arm will receive a standardized Swedish massage protocol tailored to chronic neck pain as used in [name] studies. We chose a Swedish massage protocol because they are the most widely taught and

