All outcomes will be collected at baseline, 1, 3, and 6 months. Six-month outcomes will only be collected for those who consent prior to approval of A033. For the primary outcome of Neck Disability Index (NDI) total score, we will use a linear mixed effect model with an appropriate covariance structure to compare the treatment arm to the control arm on rate of change as well as difference in outcome at the 3-month time point. Fixed effects will include treatment, time (as categorical), and treatment by time interaction. Difference in amount of change in outcome between groups at the other time points (1 and 6 months (pre A033 only)) will also be estimated and reported. We will examine the associations among the repeated measures within subjects and use a data driven approach in determining the appropriate variance-covariance structure.⁷¹ We will use the Šídák method to adjust for multiple comparisons. All analyses will include checking of assumptions and model fit. We plan intent-to-treat with the primary endpoint at 3 months and evaluation of "early" response at 1 month and "sustained" response at 6 months post-randomization (pre A033 only).

Analysis of secondary outcomes (Aim 2)

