Since this study is not specifically powered for secondary outcomes, these results should be interpreted cautiously. Pain intensity, pain interference, health-related quality of life (HRQL), depression, anxiety, and pain cognitions are all continuous measures. These subscales will be analyzed with the same approach as the primary outcome. For the pain intensity score, we will also report a clinically relevant descriptive statistic in which we define patients with > 30% reduction from baseline as "responders." For the NDI, a "responder" will be defined as a decrease of more than 5 points from baseline. This binary outcome will be observed at 1, 3, and 6 months (pre A033 only) for each participant. A generalized linear mixed model with predictors of group, time, and their interaction will be used that also includes a random subject effect to accommodate the potential correlation among observations from the same participant. The primary contrasts of interest will be the difference in proportions at 3 months between each treatment and the control group. We will use the Šídák method to adjust for multiple comparisons. Differences in proportions between treatment groups at the other time points will also be reported. For exploratory measures regression models will be used based on data type and will include pain coping, sleep problems, satisfaction, and social support.

Moderator analyses

As a secondary analysis for the primary outcome (NDI) as well as secondary outcomes, we will test baseline anxiety (GAD-7 and PTSD) and depression (PHQ-9) as moderators. This will be done separately for each potential moderator by re-running each mixed model for primary and secondary outcomes while additionally including the moderator, the moderator by treatment group interaction, and the moderator by treatment by time interaction. The treatment by time by moderator interaction represents the moderation effect on the treatment difference. If the treatment term is significant then moderation is occurring. Testing these measures as moderators will provide insight into generalizability of the interventions. For example, if the intervention loses effect in patients with high anxiety or depression, these patients may not be suited to the intervention.

Missing data

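### For anxiety by GAD-7, and depression if scored by PHQ-9, the moderator is the outcome's own baseline, which is also in the response; the listed model then gives a coding-dependent or singular result.

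*Combined protocol and SAP*

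**What the plan says.** All of this is in the combined protocol and SAP.

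- **Moderators** (8.0, Moderator analyses): "we will test baseline anxiety (GAD-7 and PTSD) and depression (PHQ-9) as moderators". The method is "re-running each mixed model for primary and secondary outcomes while additionally including the moderator", plus moderator-by-arm and moderator-by-arm-by-time. A moderator-by-time term is not listed. The three-way term is the one read as moderation.
- **Secondary outcomes** (8.0, Aim 2): "depression, anxiety, and pain cognitions are all continuous measures", and "These subscales will be analyzed with the same approach as the primary outcome".
- **Primary model** (8.0, Aim 1): "Fixed effects will include treatment, time (as categorical), and treatment by time interaction". Occasions: "All outcomes will be collected at baseline, 1, 3, and 6 months". Estimates at 1 and 6 months: "Difference in amount of change in outcome between groups at the other time points". Baseline is not listed as a covariate, and the covariance structure is to be chosen from the data.
- **Instruments** (5.0, Table 2): GAD-7 is the only scale labelled anxiety. Depression has two, "PHQ-9 Depression" and PROMIS-Depression. GAD-7 and PHQ-9 are scheduled at baseline, 3 and 6 months, with 6 months only for those enrolled before amendment A033.

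**The concern.** A model with arm, categorical time and their interaction, and no baseline covariate, can deliver a difference in change only if baseline is itself a row of the response. If the moderator M is that same baseline score, the outcome's slope on M is exactly 1 at baseline and about ρ at follow-up, where ρ is the baseline-to-follow-up correlation (equal variances). This holds in both arms, treatment effect or not: it is regression to the mean. A moderator-by-time term would absorb the common drop in slope, but none is listed, so it can be pushed into the three-way term.

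At stake is the reading of moderation for anxiety and depression. The plan intends these analyses to inform generalisability, and a significant three-way term here could reflect the model's construction and not the patients.

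**Working it through.** **Inputs.** From the documents: 100 per arm at 3 months, α = 0.05 (taken as two-sided), the fixed effects and added terms above, and a covariance structure left open. Assumed: ρ from 0.3 to 0.85, since the documents give none; a treatment effect of -0.3 SD at every follow-up; no moderation.

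**1. The plan's own figure.** n = 2(1.960 + 0.842)²/0.4² = 98.1, so 99 per group; the exact t-test needs 99.1, so 100. Power at 100 per group is 0.807 (normal) or 0.804 (t). The sample size reproduces. The plan gives no figure for the moderator analysis.

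**2. What the listed terms impose.** Let g1, g2 and g3 be the coefficients of M, M×arm and M×arm×time, with baseline and one follow-up.

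- With 0/1 arm coding, the change in slope is 0 in control (forced) and g3 in massage. The true change is -(1-ρ) in both arms. Control cannot show it, so g3 tends to -(1-ρ).
- With ±0.5 coding, the changes are forced to be -g3/2 and +g3/2. Two equal true changes cancel, and g3 averages about 0.

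The same listed terms thus give different answers under different coding, because a lower-order term is missing.

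**3. One simulated data set, random-intercept fit, 0/1 coding.** Listed terms: M 0.811, M×arm 0.189, three-way -0.336 (p = 0.00005). The massage slope is 0.811 + 0.189 = 1.000 at baseline and 1.000 - 0.336 = 0.664 at follow-up. With M×time added: M 1.000, M×time -0.379, three-way 0.043 (p = 0.70). The control slope at follow-up is then 1.000 - 0.379 = 0.621, close to massage at 0.664. The 0.811 is simply the average of control's two slopes: (1 + 0.621)/2 = 0.811.

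**4. False-positive rate of the three-way test under compound symmetry, 600 trials per cell.**

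| ρ | Listed terms, 0/1: BL+3 mo | Listed terms, 0/1: BL+3+6 mo | Mean g3 (BL+3 mo) | M×time added: BL+3 mo | M×time added: BL+3+6 mo |
|---|---|---|---|---|---|
| 0.3 | 100% | 100% | -0.70 | 5.7% | 5.7% |
| 0.5 | 100% | 100% | -0.50 | 5.3% | 5.2% |
| 0.7 | 97.8% | 99.2% | -0.30 | 3.7% | 4.3% |
| 0.85 | 81.2% | 80.5% | -0.15 | 4.0% | 3.0% |

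The mean g3 matches -(1-ρ). Repeat simulations put the 0/1 range at 78-100%, the ±0.5 range at about 6-11% (9.0% at ρ = 0.6), and the rate with M×time added at 4.5-6.5%. If software expands the three-way term over both arms, its joint test rejects in 94.5-100%, but that tests any change in slope, not a difference between arms.

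**5. Unstructured covariance.** Intercept, arm, M and M×arm fit the baseline row exactly, so its residual variance goes to 0 and the likelihood has no maximum. Holding the baseline residual SD at 0.1, 0.01, 0.0001 and 0.00000001 gives profile log-likelihoods of 394, 855, 1776 and 3618. Each tenfold cut adds 200 × ln 10 = 460.5. M×time leaves the baseline row unchanged and does not help.

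**6. Checks on scope and remedy.** A different scale as moderator, equally correlated with all occasions, gives 3.7-6.7% under the listed terms. Regressing the 3-month score on arm, baseline and arm-by-baseline gives 4.8% (5,000 trials, ρ = 0.6).

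**The case against.** Much can be said for the plan.

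- **Baseline as a response row is inferred.** No single sentence states it. If only follow-up scores were modelled, arm-by-baseline would be an ordinary interaction. The inference is still the natural one from the occasions, categorical time and change contrasts, and a clarification would settle it.
- **The high error rate depends on coding and on the missing term.** This stands. A reader might infer that the model can never separate regression to the mean from moderation. It can: under compound symmetry, moderator-by-time restores the size of the test.
- **A singular fit needs an unstructured covariance.** The plan allows that choice but does not prescribe it, so the documents do not support saying flatly that the model cannot be fitted. The promised checks of model fit would probably expose a singular matrix. They are less sure to catch the other failure: the fit in step 3 converged with only a boundary warning.
- **The harm is easy to overstate.** A reader might infer that the plan would wrongly label anxious or depressed patients as unsuited to massage. With massage coded 1 the spurious coefficient is negative, so high scorers seem to improve more on massage, the opposite of the plan's example. With control coded 1 the sign reverses. No particular wrong conclusion is built in.
- **The scope is small.** The PHQ-9 pair is conditional, because depression is named without an instrument. The plan also advises caution with secondary outcomes, but it gives power as the reason, and this fault is not one of power.

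**Conclusion.** The concern holds for one pair, GAD-7 on GAD-7, and for PHQ-9 on PHQ-9 if that is the depression outcome. As written, the three-way test for these pairs has a false-positive rate of about 78-100% (0/1 coding) or 6-11% (±0.5 coding) under compound symmetry, and no valid fit under an unstructured covariance. It is uninterpretable; it does not point to a specific wrong message.

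This rests on baseline being in the response, 100 per arm, and an assumed ρ of 0.3 to 0.85. The rate falls as ρ rises but stays far above 5% with 0/1 coding throughout that range.

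A reader might extend this to moderation of NDI or to the main treatment comparisons. The documents do not support that: the overlap arises only where moderator and outcome are the same scale, and the sample size is untouched. The missing moderator-by-time term elsewhere is a separate, milder gap. It did no harm when the moderator was equally correlated with every occasion; other patterns were not quantified.

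**What to change.** Add to Moderator analyses:

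> Where the moderator is the baseline value of the outcome (GAD-7 for anxiety, PHQ-9 for depression), baseline is removed from the response, and moderation is the arm-by-baseline interaction at 3 months in a model for the post-baseline scores that includes baseline, arm, time and their interactions.

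Or state that these pairs will not be tested. In all other moderator models, add the moderator-by-time term, so that the three-way term means the same under any arm coding. It would also help to say which depression scale is the secondary outcome.

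The cost is one or two sentences. No new data or patients are needed, the primary analysis does not change, and the analysis of these pairs becomes simpler and no longer depends on arm coding or on how a baseline row is modelled.

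### The moderator models leave out moderator by time, so an omnibus three-way test or 0/1 arm coding can report as moderation a trend that both arms share

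*Combined protocol and SAP*

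**What the plan says.** All references are to section 8.0 of the combined protocol and SAP.

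- **Base model** (Main analysis, Aim 1): "Fixed effects will include treatment, time (as categorical), and treatment by time interaction". No moderator term appears here.
- **Moderators:** "we will test baseline anxiety (GAD-7 and PTSD) and depression (PHQ-9) as moderators". Each is taken separately, for the NDI and for the secondary outcomes.
- **Terms added:** each mixed model is re-run "additionally including the moderator, the moderator by treatment group interaction, and the moderator by treatment by time interaction".
- **Meaning given to the three-way term:** "The treatment by time by moderator interaction represents the moderation effect on the treatment difference".
- **Decision rule:** "If the treatment term is significant then moderation is occurring".
- **Use of the result:** "For example, if the intervention loses effect in patients with high anxiety or depression, these patients may not be suited to the intervention".

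The two lists together give every fixed effect of the moderator model, and moderator by time is not among them. Nothing elsewhere supplies it. For moderation, the plan states no arm coding, no degrees of freedom and no contrast.

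**The concern.** A three-way interaction measures a difference between arms only if the model lets the moderator's slope change over time in both arms. Without moderator by time, that shared change has to go somewhere.

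- **Arm and time as class factors.** Software fills the gap by expanding the three-way term to moderator-by-time columns for both arms. With baseline, 1 and 3 months that is 4 columns instead of 2. The omnibus test then asks whether the score predicts change in either arm.
- **Arm as a 0/1 variable with product terms.** The moderator's slope in the arm coded 0 is forced to be constant over time. The three-way coefficient becomes the moderator-by-time slope in the arm coded 1 alone.

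In both cases a baseline score that is merely prognostic of change can look like an effect modifier. Suppose high scorers improve less in both arms. With massage coded 1, the 0/1 model shows massage losing its effect in them, which is the plan's own example of patients who may not suit the treatment. With control coded 1, the same data point the opposite way.

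**Working it through.** **Inputs from the plan.** 100 per group at 3 months, a 0.4 SD difference in change, Type I error 0.05 and 80% power (Sample size and power). Two arms; visits at baseline, 1 and 3 months, with 6 months only for those enrolled before A033.

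**The plan's own figure.** n per arm = 2(1.96 + 0.84)^2 / 0.4^2 = 98, or 99 with unrounded normal quantiles. The exact t-test gives 99.08, so 100 per group is reproduced. The plan gives no figure for the moderator analysis.

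**Assumptions.** The documents give no slope or correlation. Assumed: unit SD at each visit, equal correlation 0.5 between visits, complete data, a standardised moderator, and no true moderation. The shared slope g is the SD of 3-month change per SD of moderator, equal in both arms, with half of it present at 1 month.

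**0/1 coding, 3-month term.** The term estimates the slope in the arm coded 1 only.
- Variance of change = 2(1 - 0.5) = 1, so SE = sqrt(1/100) = 0.1.
- The expected estimate is g, although the true moderation is 0.
- Rejection = P(Z > 1.96 - g/0.1) + P(Z < -1.96 - g/0.1). At g = 0.2 this is P(Z > -0.04) + P(Z < -3.96) = 52%.

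**Class factors, omnibus test (4 df).**
- The changes at 1 and 3 months have covariance [[1, 0.5], [0.5, 1]].
- For the slope vector (0.5g, g), noncentrality per arm = 100g^2(0.25 - 0.5 + 1)/0.75 = 100g^2. Over two arms it is 200g^2.
- For g = 0.05, 0.1, 0.2 and 0.3 that is 0.5, 2, 8 and 18. The 5% critical value of chi-square on 4 df is 9.49.

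| Shared slope | Omnibus, formula | Omnibus, simulated | 0/1, formula | 0/1, simulated |
|---|---|---|---|---|
| 0.05 | 8% | 8% | 8% | 9% |
| 0.1 | 17% | 17% | 17% | 16% |
| 0.2 | 60% | 60% | 52% | 51% |
| 0.3 | 94% | 94% | 85% | 84% |

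A separate simulation with an estimated unstructured covariance gave 15%, 58% and 93% (omnibus) and 17%, 49% and 83% (0/1, 3-month term) at slopes 0.1, 0.2 and 0.3. At correlation 0.7 and slope 0.2 the rates rise to 85% and 73%.

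**With moderator by time added.** Over slopes 0 to 0.3 and correlations 0.5 and 0.7, rejection is 4.0% to 5.5% for the joint test and 3.7% to 5.6% for the 3-month term. The mean estimate is about 0.

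**Where the omission does little or no harm.**
- An explicit between-arm slope contrast at 3 months in the class-factor model: about 4% to 6%.
- Symmetric arm coding (+/-0.5 or -1/+1) with equal arms: about 4% to 7%. With 90 against 110 and +/-0.5 coding: 6.1% to 6.7% at slope 0.2 and 7.2% to 8.2% at 0.3.
- A prognostic effect of 0.5 SD that is constant over time: 4.7% to 6.0% (0/1) and 4.2% to 5.8% (omnibus).

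**The case against.** **The plan may intend the safe contrast.** It sets the primary endpoint at 3 months, refers to a contrast from the mixed model, and describes the three-way term as acting on the treatment difference. An analyst who codes arm as a class factor and tests the 3-month difference in slopes between arms gets a valid answer. This stands as a limit on the point. It does not remove it, because the moderation paragraph names no such contrast and its decision rule leaves the omnibus test open. Numeric 0/1 coding is the less likely of the two failures, since the plan treats time as categorical and nowhere suggests numeric arm coding.

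**The term might be implied by hierarchy.** The plan spells out the other lower-order moderator terms and omits this one, so a programmer following the text would leave it out.

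**The size is assumed.** This stands. At a shared slope of 0.05 the rates are only 8% to 9%, and with no shared trend they are about 5%.

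**The plan has cautions and checks.** It calls for caution on secondary outcomes because of low power, and for checks of model fit. Caution about power does not correct a biased coefficient, and fit checks might reveal the missing term but need not.

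**A reader might infer that real moderation will be hidden.** Under 0/1 coding with massage coded 1, a true moderation of +0.3 with a shared slope of -0.3 gives a massage-arm slope of 0.3 - 0.3 = 0, so detection falls to about 5%. That is exact cancellation, a constructed worst case. With shared slopes of -0.2 and -0.1, detection is 17% and 48%, against roughly 55% with the term added. It is not a typical consequence.

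**The simulated design does not fit every outcome.** The Main analysis paragraph says "All outcomes will be collected at baseline, 1, 3, and 6 months", but Table 2 shows no 1-month visit for PHQ-9 or GAD-7, and responder status has no baseline value. The mechanism carries over; the exact rates do not.

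**Conclusion.** The point holds as a conditional specification error. The listed model omits a term that its stated interpretation needs, and two ordinary implementations then confuse a shared prognostic trend with moderation. False moderation is near nominal at a shared slope of 0.05, about one trial in six at 0.1, and 51% to 60% at 0.2, given 100 per arm and correlation 0.5. The slopes and the correlation are assumptions.

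A reader might infer that the moderator results will be wrong however they are programmed, or that the primary result is in doubt. The documents support neither. The error needs both a score that predicts change over time and one of the two failing implementations, and only the secondary moderator analyses are touched. A reader might also take the decision rule to mean a test of the treatment main effect. The sentence before it names the three-way interaction, so loose wording is more likely. The change is worth making before analysis, but it is not critical to the trial's main conclusion.

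**What to change.** 1. Add moderator by time to every moderator model.
2. For continuous outcomes, name the 3-month moderator by treatment by time contrast as the test of moderation, that is, the between-arm difference in the moderator's effect on change from baseline to 3 months. With the added term, this contrast does not depend on how arm is coded.
3. For the responder models, which have no baseline outcome, name the between-arm difference in the moderator's effect at 3 months. With reference coding of arm and visit, that is the moderator by treatment coefficient plus the 3-month three-way coefficient.
4. In the decision rule, replace the reference to the treatment term with the named contrast, so that it agrees with the sentence before it.

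The cost is SAP wording and one more fixed effect per model (one coefficient for each visit after the reference visit), estimable from data already being collected. The sample size does not change.

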New modification sample size: For the comparison of the TT-M and the waitlist control group (WL-C) we need 100 patients per group ($N = 200$) by 3 months to have 80% power to detect a 0.4 SD difference in change in NDI from baseline between TT-M and control with Type I error = 0.05 for the comparison of interest: TT-M vs WL-C. All analysis will be conducted under the intention-to-treat principle. Sample size was derived based on an independent two-sample t-test which is conservative compared to the contrast from our proposed linear mixed model.

Previously we assumed a total attrition for the TTM and WL-C arm of $(27+20)/(98+99) = 47/197 = 24\%$, thus we sought to enroll a Total $N = 264$ ($200/.76$) or 132 per group in the TT-M and WL-C study groups. We will now enroll Total $N = 296$ ($264 + 16 \times 2$) so that we will

have an additional 16 in the TTM arm to account for the 16 that were paused due to COVID but will also maintain the current randomization allocation. For IRB purposes, we will continue to recruit to reach at most N = 308 this would increase the 16 COVID paused to also account for potential 24% attrition (16/.76 = 22 per group). However, this is not necessarily required as the COVID paused will still be included in the linear mixed model up until their one month assessment. This should allow us to reach our sample size of 100 per group to complete the 3 month assessment.

Data analysis: Baseline characteristics of TOMCATT sample

As an RCT, we expect characteristics of study participants to be balanced across the two study arms. We will compare all baseline demographic and clinical characteristics between the treatment groups using the appropriate test (ie, ANOVA, Kruskal-Wallis test, or Chi-square test). Variables found to significantly differ will be included in subsequent regression models.

Main analysis (Aim 1) of the primary outcome (NDI total score)

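### The moderator analysis names the three-way interaction as the moderation effect, then judges moderation by the treatment term, which does not test it; the listed model also omits moderator-by-time

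*Combined protocol and SAP*

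**What the plan says.** The primary analysis in Section 8.0 is a linear mixed model: "Fixed effects will include treatment, time (as categorical), and treatment by time interaction". Baseline is one of the outcome times: "All outcomes will be collected at baseline, 1, 3, and 6 months" (6 months only for those enrolled before amendment A033).

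Under Moderator analyses, "we will test baseline anxiety (GAD-7 and PTSD) and depression (PHQ-9) as moderators". Each is tested separately, for the primary and the secondary outcomes, by "additionally including the moderator, the moderator by treatment group interaction, and the moderator by treatment by time interaction". Moderator-by-time is not in that list.

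Two adjacent sentences then give the interpretation. The first is "The treatment by time by moderator interaction represents the moderation effect on the treatment difference". The second is "If the treatment term is significant then moderation is occurring". The section closes with a hypothetical example: if benefit is lost at high anxiety or depression, "these patients may not be suited to the intervention".

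The section does not state the reference visit, whether moderator scores are centred, or the significance level for these tests.

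**The concern.** The first of the two sentences is right and the second contradicts it. In this model the treatment coefficient is an arm difference at moderator score zero, either at the reference visit or averaged over visits, depending on coding. It does not measure whether the arm difference changes with GAD-7, PTSD or PHQ-9. Yet it is the only criterion the section gives, and an analyst following the text would apply it.

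Two errors become possible. Where the treatment term responds to benefit, a massage effect that is the same in everyone can be reported as moderated. Where it does not, real moderation goes unseen. The rule applies to three moderators across the primary and secondary outcomes, and the findings are meant to inform who the intervention suits. If the contradiction stays, the deciding term can be chosen after the results are known.

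**Working it through.** **Inputs from Section 8.0.** 100 evaluable per arm at 3 months, effect 0.4 SD of change in NDI, Type I error 0.05, 80% power ("we need 100 patients per group ($N = 200$) by 3 months to have 80% power").

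**Assumptions not in the documents.** Two-sided 0.05; visits at baseline, 1 and 3 months; SD of change = 1; equal within-person correlation ρ between visits, so the variance at one visit is 1/(2(1−ρ)); a normally distributed moderator with SD 1; an uncentred score has its mean 1.5 SD above zero. The rejection rate is P(z) = Φ(z − 1.96) + Φ(−z − 1.96).

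**1. The plan's own figure.** SE = √(2/100) = 0.1414 and z = 0.4/0.1414 = 2.83, so P = 81% (80.4% with the exact t-test). The stated sample size is reproduced.

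**2. Uniform benefit of 0.4 SD, no moderation: how often does the treatment term fire?** With an uncentred score the coefficient is the effect at score zero. Its variance is multiplied by 1 + 1.5² = 3.25, so z is divided by 1.803.

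| Meaning of the treatment term | Centred | Uncentred |
|---|---|---|
| Main effect, baseline as reference (expected value 0 by randomisation) | 5% | 5% |
| Main effect averaged over the three visits, same effect at 1 and 3 months, ρ = 0.5 | 64% | 25% |
| The same, ρ = 0.7 | 37% | 15% |
| Main effect, 3 months as reference, ρ = 0.6 | 72% | 29% |
| Treatment effect on 3-month change | 81% | 35% |

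- Averaged over visits: the mean effect is 0.4 × 2/3 = 0.267 and the variance of a visit mean is (1 + 2ρ)/(3 × 2(1−ρ)). At ρ = 0.5 that is 0.667, so z = 0.267/√(0.667 × 0.02) = 2.31. At ρ = 0.7 it is 1.333, so z = 1.63. With no effect at 1 month and ρ = 0.7, z = 0.133/0.163 = 0.82 and the rate is 13%.
- 3-month reference: the SD at one visit is √1.25 = 1.118, so z = 0.4/(1.118 × 0.1414) = 2.53.
- The table's uncentred column assumes moderator-by-time is in the model. Without it, as the plan lists the terms, the last entry is 0.4/√(0.0325 + 0.01) = 1.94, or 49%.

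Simulation of the listed model (2,000 trials per setting, ρ = 0.5 and 0.7) agrees: 4.8% to 5.4% with baseline as reference; 64% and 37% averaged, centred; 25% and 16% averaged, uncentred; 80% to 81% and 47% to 49% for 3-month change. The three-way interaction fires in 4.3% to 5.7%.

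**3. Real moderation of 0.4 SD of change per SD of moderator.**

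- No average effect, centred score: the expected treatment coefficient is zero in every reading, so detection is about 5% (simulated 4.5% to 5.2%).
- No average effect, uncentred score: the coefficient is non-zero because the effect at score zero is 0.4 × 1.5 = 0.6 SD in size. It fires in 47% (averaged) or 83% (3-month change) of runs, but stays at about 5% with baseline as reference.
- Average effect of 0.4 SD as well, baseline as reference: still only 5% to 6%.
- Three-way contrast at 3 months with moderator-by-time in the model: SE = 0.1414 and z = 2.83, so about 80%.

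**4. Is changing the decision rule enough?** Without moderator-by-time, and with baseline-reference coding, the control arm's moderator slope is forced to be constant over time. The three-way coefficient then comes from the massage arm alone, with SE = 1/√100 = 0.1. Suppose the effect is uniform but the moderator predicts change by 0.2 SD per SD in both arms. Then z = 0.2/0.1 = 2 and P = 52%. Simulation of the joint three-way test gave 53%, and 5% once moderator-by-time was added.

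**The case against.** The strongest reply is that this is a drafting slip. The sentence just before names the right term, the model is extended expressly to add moderator interactions, and the example that follows describes an interaction. A reader might infer that the team has settled on testing the wrong term. The documents do not support that; what they show is a contradiction between adjacent sentences. It still needs resolving, because the incorrect sentence is the one that states the rule.

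A reader might also infer that a uniform benefit is *likely* to be reported as moderated. That is too strong. Baseline is an outcome time, and with baseline as reference the rate is only the nominal 5%. Most uncentred rates are below one half. The 80% figure requires reading the treatment term as a treatment-by-time contrast. The averaged figures move with the assumed correlation and 1-month effect.

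Nor do the documents tie the remark about unsuitable patients to the overall treatment effect. It is a hypothetical, conditional on benefit being lost at high anxiety or depression, and a significant treatment term alone would not show such a loss.

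Finally, the analysis is labelled secondary, and the primary 3-month comparison and the sample size do not depend on it. That limits the stakes, but it does not make the rule valid.

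**Conclusion.** The point holds as an internal contradiction in which the stated decision rule is wrong as written. Under every reading the treatment term fails as a test of moderation, though not always in the same direction. It either responds to a uniform benefit, at rates up to about 80%, or, with baseline as reference, stays near 5% whether or not moderation exists. For a centred score and no average effect, real moderation is caught in about 5% of trials against about 80% for the 3-month three-way contrast.

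These sizes rest on the plan's 100 per arm and 0.4 SD, plus the assumed correlation, moderator distribution, 1-month effect and mean of the uncentred score. The conclusion that the treatment term is not a test of moderation rests on none of them. The 53% in the last step depends on an assumed prognostic effect of 0.2 SD per SD and shows the mechanism only. The correction should be made before analysis; the primary result is unaffected.

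**What to change.** In Section 8.0, Moderator analyses:

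1. Replace the decision rule with: *Moderation is judged from the treatment-by-moderator interaction on change from baseline to 3 months (the 3-month component of the treatment by time by moderator term), reported with its estimate and 95% CI; the treatment term is not used.*
2. Add moderator-by-time to the listed model terms, so that a purely prognostic moderator-by-time effect is not read as moderation.
3. State the reference visit and whether moderator scores are centred.
4. Rest any statement about which patients may not be suited to the intervention on that contrast.

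The cost is one replaced sentence, one added model term and a short note on coding. No data collection, sample size or primary analysis changes. Power for the contrast will be lower than the listed model suggests (about 80% rather than 98% to 99% for 0.4 SD per SD), because the higher figure comes from forcing the control arm's moderator slope to be constant over time.
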